1	
2	
3	
4	
5	RESEARCH PROTOCOL
6	
7	Medical Ethics Committee at VU University Medical
8	Centre, Amsterdam
9	
10	Ethical approval for this study was obtained from the Medical Ethical Committee of the VU University
11	Medical Center in Amsterdam, The Netherlands (NL60315.029.17, registration number 2017.418).
12	
13	
14	
15	Title: Cost-effectiveness of a tailored lifestyle intervention in patients with serious mental illness: the
16	SMILE study
17	
18	Coordinating investigator/project leader [name] ([contact])
19	
20	
21	
22	
20	
23	
24	
) E	
25 26	
20 27	
28	

₃₈ 39	SMALL CHANGES MADE TO THE ORIGINAL PROTOCOL
40	Sample size: We planned to include 260 participants taking into account 20% drop-out, but finally
41	included 224 participants in the study. It is unlikely that 36 extra participants would substantially
42	change our results and conclusion. A larger sample size would have resulted in a more precise effect
43	estimate (smaller 95% CI) but would probably not have changed the estimate itself.
44	Participating FACT-teams: Initially we planned on including 18 FACT-teams, but a total of 21
45	FACT-teams joined the study.
46	

Formatted: Num

INTRODUCTION AND RATIONALE

Cardiovascular disease is one of the leading causes of the estimated 20-25 years reduced life expectancy for persons with serious mental illness (SMI) [1-6]. This excess cardiovascular mortality is primarily attributable to obesity, diabetes, hypertension, dyslipidemia and lifestyle factors [7]. Additionally, cardiovascular disease in persons with SMI contributes to enormous societal costs. In the Netherlands, €19.6 billion were spend on the treatment of mental disorders (22% of the total spend on care in 2011), cardiovascular disease comes in second place with €8.3 billion (). The reduction of these cardiovascular risks has been associated with performing lifestyle interventions [8-12].

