138	disorders, mood disorders (including bipolar disorder), severe personality disorders and addition
139	disorders.
140	Adults (≥18 years) with SMI in care by Flexible Assertive Community Treatment (FACT) teams in the
141	Netherlands will be included. The study aims to recruit 260 patients in total (for more information
142	regarding the power calculation, see chapter 3.4). The prevalence of persons with SMI is 1.3%
143	(n=216.000) of the total population and 1.6% (n=160.000) of the population of \geq 18 and 65 years in
144	the Netherlands in 2013. About 75% is cared for by the GGZ (Mental Health and Addiction Care
145	institutes) or other providers [16]. In the Netherlands there are approximately 250 certified FACT-
146	teams.
147	
148	Inclusion criteria
149	In order to be eligible to participate in this study, a subject must meet all of the following criteria:
150	• patient with SMI
151	• age ≥18
152	• body mass index ≥27
153	 willing to and able to sign informed consent (mentally competent)
154	
155	Exclusion criteria
156	A potential subject who meets any of the following criteria will be excluded from participation in this
157	study:
158	• Contra-indications (to be assessed by the treating physician/psychiatrist) for participation due
159	to acute psychiatric crisis or somatic diseases (e.g. bariatric surgery, cancer, heart attack or
160	stroke)
161	Subjects with a cognitive impairment sufficient to interfere with their ability to provide

informed consent, complete study questionnaires, or participate in a group intervention.

127 128

162

STUDY POPULATION

163 Women who are pregnant, breastfeeding, or planning a pregnancy during the course of the 164 study 165 Subjects not able to communicate in the Dutch language 166 167 Sample size calculation 168 This trial is powered to detect a mean difference of 4 kilograms in weight reduction after 1 year 169 between the intervention and usual care group [10, 17]. This difference is based on the outcomes of 170 multiple clinical trials including STRIDE, ACHIEVE and PREMIER [10, 14, 15, 17, 18]. using a 171 power of 0.80, an alpha of 0.05 and an SD of 10 two groups of 100 patients are needed to detect a 172 difference of 4 kilograms. Assuming an ICC of 0.01 for clustering of persons with SMI within a 173 FACT-team, and a dropout rate of 20% [10, 14, 15], the aim is to recruit 260 patients in total. 174 175 176 177

TREATMENT OF SUBJECTS

Investigational treatment

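### With 224 participants in 21 teams, the protocol's own inputs give about 73% power for 4 kg rather than 80%, yet the change note calls the shortfall immaterial without restating power

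*Protocol*

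**What the plan says.** The section on sample size calculation sets the target: "This trial is powered to detect a mean difference of 4 kilograms in weight reduction after 1 year". It then gives a "power of 0.80, an alpha of 0.05 and an SD of 10 two groups of 100 patients are needed to detect a" difference of that size. Clustering and attrition are added in one sentence: "Assuming an ICC of 0.01 for clustering of persons with SMI within a" FACT-team, "and a dropout rate of 20% [10, 14, 15], the aim is to recruit 260 patients in total". The section gives no cluster size, number of teams or design effect.

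The note at the front on small changes to the original protocol supplies the rest. On numbers: "We planned to include 260 participants taking into account 20% drop-out, but finally" 224 were included. On teams: "Initially we planned on including 18 FACT-teams, but a total of 21" took part. On the consequence: "It is unlikely that 36 extra participants would substantially" alter the results and conclusion. The reason offered is that a larger sample would have narrowed the 95% confidence interval but probably left the estimate where it was. No power or detectable difference is recalculated, so 0.80 remains the only power figure in the document.

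**The concern.** Two things do not fit together.

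- **The reassurance answers a different question.** Sample size is not expected to shift an unbiased estimate. It does set the width of the interval, and the width decides whether zero is excluded. In a trial powered for a significance test on 4 kg, that bears directly on the conclusion.
- **The inflation from 200 to 260 looks too small.** Dropout alone takes 200 to 250, which leaves little room for clustering with only 18 teams.

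If nothing is restated, a non-significant result will be read against a claimed 80% chance of detecting 4 kg, when the protocol's own assumptions imply a lower chance for the sample obtained.

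**Working it through.** **Inputs.** From the sample size section: difference 4 kg, SD 10 kg, alpha 0.05 (taken as two-sided, which reproduces the stated figure), power 0.80, 100 per group, ICC 0.01, dropout 20%, target 260. From the change note: 18 teams planned, 21 obtained, 224 participants included. Cluster size is derived as completers divided by teams, with equal team sizes and 1:1 allocation assumed.

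**Step 1: the individually randomised figure.** n per group = 2(1.96 + 0.8416)² × 10² / 4² = 98.1, or 99.1 with the t distribution. The stated 100 is right.

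**Step 2: the inflation to 260.**
- Dropout alone: 200 / 0.8 = 250.
- Completers from 260: 260 × 0.8 = 208. Implied design effect: 208 / 200 = 1.04. Solving 1 + (m − 1) × 0.01 = 1.04 gives m = 5 completers per team.
- With 18 teams: m = 208 / 18 = 11.6, so the design effect is 1 + 10.56 × 0.01 = 1.106.
- Completers needed when cluster size grows with N: N = B × 0.99 / (1 − 0.01 × B / 18), where B is the total before clustering. B = 200 gives 222.75, and 222.75 / 0.8 = 278.4. B = 198.2 (2 × 99.1) gives 220.4, and 220.4 / 0.8 = 275.6. The target should have been about 276 to 278.

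**Step 3: power.** Effective N = completers / design effect. SE = 10 × √(4 / effective N). Normal power = Φ(4 / SE − 1.96). The t version uses a noncentral t with teams − 2 degrees of freedom.

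| Sample | Dropout | Completers | Per team | Design effect | Effective N | Power (normal) | Power (t) |
|---|---|---|---|---|---|---|---|
| 260 in 18 teams | 20% | 208 | 11.6 | 1.106 | 188.1 | 78.3% | 73.1% (16 df) |
| 260 in 21 teams | 20% | 208 | 9.9 | 1.089 | 191.0 | 78.9% | 74.6% (19 df) |
| 224 in 21 teams | 20% | 179.2 | 8.5 | 1.075 | 166.6 | 73.3% | 68.8% (19 df) |
| 224 in 21 teams | 10% | 201.6 | 9.6 | 1.086 | 185.6 | 77.8% | 73.4% (19 df) |
| 224 in 21 teams | 0% | 224 | 10.7 | 1.097 | 204.3 | 81.6% | 77.4% (19 df) |

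**Step 4: detectable difference.** For 224 in 21 teams at 20% dropout, SE = 10 × √(4 / 166.6) = 1.549 kg. With 80% power the detectable difference is 2.8016 × 1.549 = 4.34 kg.

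**Step 5: what the missing 36 cost.** Holding 21 teams and 20% dropout fixed, power falls from 78.9% to 73.3%, or 5.6 points. The interval half-width grows from 1.96 × 1.447 = 2.84 kg to 1.96 × 1.549 = 3.04 kg, about 7% wider. The rest of the gap below 80% comes from the target itself.

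**The case against.** - **The shortfall is disclosed.** The note reports 260 against 224 and 18 against 21 teams, and concedes a wider interval. This stands: the change in numbers is not an error. Only the inference drawn from it is unsupported. The note looks back and may rest on results not shown, but it cites none and argues only from the estimate.
- **Actual dropout is unknown.** A reader might infer that the trial's real power is around 70%. The documents do not support that. The 73% applies the planned 20% dropout to the recruited sample; with no dropout, power on the normal approximation would exceed 80%. The figure is conditional and should be reported with its range.
- **The analysis may do better than the calculation.** Weight is scheduled at baseline, 3, 6 and 12 months, and linear mixed models with covariates are planned. That could use partial data and reduce residual variance. The gain cannot be quantified from the protocol, and unequal team sizes would work the other way.
- **The 260 target is nearly adequate.** A reader might infer that the design was materially underpowered from the start. On the normal approximation it gives 78.3%, less than two points short. The 73.1% needs between-team degrees of freedom, which the protocol does not specify and which a statistical analysis plan may settle. The 18 teams also appear only in the change note. What stands is narrower: 260 does not follow from the stated inputs at the planned number of teams.
- **Recalculated power is of limited use once recruitment has closed.** The interval will carry the precision. That is fair, but it does not justify saying that the sample size has no bearing on the conclusion.

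**Conclusion.** The point holds at moderate weight. Under 4 kg, SD 10, ICC 0.01, 20% dropout and equal team sizes, the sample obtained gives 73% power on the protocol's own kind of approximation, about 7 points below the stated figure; with 19 degrees of freedom it is 69%. The reassurance about the missing 36 participants does not follow from the reason given. The target of 260 is a secondary and smaller defect: about 6 to 7% too few participants (276 to 278 against 260), costing under 2 points of power on the normal approximation.

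Nothing here shows that the trial's estimate or conclusion is wrong, or that more patients should be recruited. How far achieved power falls below 80%, or whether it does on the normal approximation, depends on a dropout rate that the document does not give.

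**What to change.** 1. **Change note.** Replace the sentence on 36 extra participants, and the argument supporting it, with wording such as: *With 224 participants in 21 teams, SD 10, ICC 0.01 and the planned 20% dropout, power to detect 4 kg is about 73% (69% using between-team degrees of freedom), and about 4.3 kg is detectable with 80% power on the normal approximation. With 10% or no dropout, power is about 78% or 82% (73% or 77%).* If actual dropout is known, add the figure for it.
2. **Sample size section.** Leave the planning statement as it stands and add a dated annotation: 18 teams, about 11.6 completers per team, design effect about 1.11. State that 260 in 18 teams gives about 78% power (about 73% with 16 degrees of freedom), and that about 276 to 278 would have been needed for 80% on the normal approximation.

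The cost is wording only, with no change to recruitment, data or analysis. The stated power becomes less favourable.

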99 100 The study will consist of an economic evaluation alongside a cluster randomized controlled trial using 101 a 1 year follow-up. Effectiveness and cost-effectiveness of the tailored lifestyle intervention will be 102 evaluated in comparison with usual care. Before the persons with SMI are recruited, participating 103 FACT-teams will be randomly allocated to the tailored lifestyle intervention or usual care. 104 105 The study will be carried out in two parts. At first, half of the centres will start with the trial and about 106 6 months later, the other centres will start. The tailored lifestyle intervention lasts 12 months in total. 107 Including inclusion of participants, analysis and reporting phase, the total duration of the SMILE study 108 will be 48 months. 109 110 JUSTIFICATION STUDY DESIGN 111 Randomization will be performed at the level of the FACT teams. All persons with SMI receive the 112 same treatment within a cluster (FACT team). Major reason for this randomization procedure is to 113 avoid contamination of the treatment within the same FACT team. It is not possible to blind persons 114 with SMI and FACT team professionals to the allocated intervention due to the nature of the tailored 115 lifestyle program. However, the pragmatic design of the study enhances the external validity. Staff 116 from FACT teams in the usual care control group will not be trained to perform the tailored lifestyle 117 intervention until after the end of the trial. That way, FACT team members cannot unintentionally 118 apply aspects of the intervention to their usual care for the SMI patients. 119 120 121 122

98

STUDY DESIGN

129	Population (base)
130	SMI is defined according to the consensus paper by Delespaul and the consensus group SMI [16].
131	Persons have SMI when: - there is a psychiatric disorder which requires long-term treatment and care
132	(symptomatic not in remission); - and which is accompanied by severe impairment in social
133	interaction and / or social functioning (non-functional remission); - the severe impairment is the cause
134	and effect of a mental illness; - it is structurally c.q. a long time, at least several years; - coordinated
135	care from professionals in care networks is indicated to realize the treatment plan. The consensus
136	group also stated that SMI cannot be limited to certain psychiatric diagnoses. The most prevalent
137	psychiatric disorders in the group of patients with SMI are: schizophrenia and related psychotic

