333	Randomisation, blinding and treatment allocation
334	RANDOMISATION
335	Before persons with SMI are recruited, participating FACT-teams will be randomly allocated to serve
336	as intervention condition (where the tailored lifestyle intervention will be implemented) or control
337	FACT-teams (where care as usual will be given). Patients will be allocated to either one of the
338	treatment conditions, based on the FACT-teams that treated them.

339	Randomisation will be stratified by centers. This is done to ensure the comparability between FACT
340	teams and therefore reduce bias. The randomization results will be communicated to the participating
341	FACT-teams by the researchers.
342	Randomisation will be performed by a statistician blinded to the characteristics of the FACT-teams
343	using a computer generated list of random numbers.
344	BLINDING
345	Blinding of patients and FACT-team members is not possible due to the nature of the intervention.
346	The statistician and health economist will be blinded for the allocation of the intervention by keeping
347	the information of the allocation of the intervention in a separate data file.
348	The assessors of measurements will also not be blinded, because if they are employed by the FACT-
349	team they will know whether the fact team provides the lifestyle intervention or not.
350	
351	Study procedures
352	Assessments will be made according to the schedule listed below.
353	
354	

Registry Schedule of Assessments

	Baseline	3 months	6 months	12 months
DEMOGRAPHICS				
Age, ethnicity, gender	X			
Height (cm)	X			
Weight (kg)	X	X	X	X
Marital status	X			X
Education level	X			X
Employment status	X			X
Diagnosis of SMI	X			X
PRIMARY OUTCOME				
Weight loss	X	X	X	X
ANTHROPOMETIC MEA	SURES			
BMI (kg/m²)	X	X	X	X
Central Obesity (cm)	X	X	X	X
PATIENT REPORTED QU	J ESTIONNAIR I	ES		
SF12	X		X	X
PAM	X		X	X
Smoking status	X		X	X
COSTS				
Cost questionnaire	X		X	X
CLINICAL MEASUREME	ENTS			
HDL Cholesterol (mmol/l)	X			X
LDL Cholesterol (mmol/l)	X			X
Total Cholesterol (mmol/l)	X			X
Triglyceride (mmol/l)	X			X
Glucose metabolism (mmol/l)	X			x
Systolic BP (mm/hg)	X		X	X
Diastolic BP (mm/hg)	X		X	X
OTHER				
Intervention appointments not attended		Weekly	monthly	
Prescribed medication	X		X	X
Admission Mental health ward	x		X	x

356 357

STATISTICAL ANALYSIS

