Characteristics of the patients in the treatment groups will be presented using descriptive statistics (mean (standard deviation), median (range) or (proportion)) to determine whether randomization was successful; i.e., to assess if balanced groups were obtained after randomization. All analyses will be on an intention-to treat basis.

Primary study parameter(s)

DATA-ANALYSIS AND PRESENTATIONS/SYNTHESIS

Differences between the tailored lifestyle intervention group and the usual care group will be tested using mixed methods analyses. To test the hypothesis that the tailored lifestyle intervention is more effective than usual care in reducing weight loss (primary outcome) over time, linear mixed models will be used. The obtained beta's describe the reduction in kilograms in the intervention group relative to the control group. Mixed model analyses can correct for clustering of data within the participating centres by adding "levels" to the analysis. The main analysis will consist of fully corrected models, which will be corrected for significant differences between the two groups at baseline. We will also evaluate whether dose, defined as the number of intervention sessions and number of telephone contacts, is related to change in the outcomes across time among participants who receive the intervention. We will include gender, age, and other variables that are known to affect weight as covariates in all analyses.

Secondary study parameter(s)

Secondary outcomes will be analysed as the primary data analysis. If necessary, logistic mixed models will be performed instead of linear mixed models depending on the outcome.

Other study parameters. Economic evaluation. Process evaluation.

Other parameters are presented as follows: ethnicity (categorical), age (continuous), gender (dichotomous), diagnosis of SMI (categorical), completed education (categorical), marital status (categorical) and employment status (categorical).

COST EFFECTIVENESS ANALYSIS

388 General considerations

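### The analysis text names the centre as the clustering level, although the FACT team is the randomised unit; a model with centre alone would understate the standard error

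*Protocol*

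**What the plan says.** - **Unit of randomisation** (Protocol, Justification study design): "Randomization will be performed at the level of the FACT teams". All patients of one team receive the same treatment.
- **Role of centre** (Protocol, Randomisation): "Randomisation will be stratified by centers". The stated purpose is to make the FACT teams comparable, so centre and team are two different levels.
- **Sample size** (Protocol, Sample size calculation): "Assuming an ICC of 0.01 for clustering of persons with SMI within a" FACT-team, together with a 4 kg difference, an SD of 10, power 0.80, alpha 0.05 and 20% dropout.
- **Analysis** (Protocol, Statistical analysis, Primary study parameter(s)): linear mixed models for weight, then "Mixed model analyses can correct for clustering of data within the participating centres". The sentence ends by saying that this is done by adding levels, in the plural, and does not list them. This is the only statement on clustering in the effectiveness analysis.
- **Secondary outcomes** (same section) follow the primary analysis, with logistic mixed models where the outcome requires it.

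**The concern.** Each team lies wholly in one arm, so variation between teams goes straight into the comparison of arms. Centre behaves differently. With randomisation stratified by centre, a centre will generally hold teams of both arms, and differences between centres largely cancel from the treatment contrast. A centre intercept therefore removes variance that does little harm and leaves between-team variance in the residual, where the model treats it as independent patient-level noise.

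An analyst who follows the named level literally would report standard errors that are too small, intervals that are too narrow and a type I error above 5%, for weight and for every secondary outcome. The analysis would also fail to match the sample size, which already allows for team clustering.

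**Working it through.** **Inputs from the protocol.** Difference 4 kg, SD 10, power 0.80, alpha 0.05 (taken as two-sided), 100 per group, ICC 0.01 within team, 20% dropout, 260 planned; 18 teams planned and 21 joined; 224 patients included. **Not in the protocol, so assumed:** the number of centres, any ICC other than 0.01, equal team sizes, and 20% dropout applied to the 224.

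**Step 1: the plan's own figure.** n per arm = 2 × (1.96 + 0.84)² × 10² / 4² = 98, or 99 with unrounded quantiles and rounding up; the stated 100 reproduces. Dropout alone would turn 200 into 200/0.8 = 250, or 200 × 1.2 = 240. The stated 260 exceeds both, so it contains an allowance for clustering. For example, with 21 teams, m = 200/21 = 9.52, the design effect is 1 + 8.52 × 0.01 = 1.085, and 200 × 1.085 × 1.2 = 260. The ICC behind that allowance is at team level. (How dropout was applied is a separate matter.)

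**Step 2: team variance left out.** With m analysed patients per team:

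- design effect DE = 1 + (m − 1) × ICC
- actual type I error ≈ 2 × (1 − Φ(1.96/√DE))
- shortfall of the reported standard error = 1 − 1/√DE

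| Analysed / teams | m | DE at ICC 0.01 | SE too small by | Type I, ICC 0.01 | ICC 0.03 (assumed) | ICC 0.05 (assumed) |
|---|---|---|---|---|---|---|
| 208 (260 × 0.8) / 18 | 11.6 | 1.106 | 4.9% | 6.2% | 8.8% | 11.3% |
| 260 / 18 | 14.4 | 1.134 | 6.1% | 6.6% | 9.8% | 13.0% |
| 179 (224 × 0.8) / 21 | 8.5 | 1.075 | 3.6% | 5.9% | 7.7% | 9.5% |
| 224 / 21 | 10.7 | 1.097 | 4.5% | 6.1% | 8.4% | 10.8% |

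First row in full: m = 208/18 = 11.56; DE = 1 + 10.56 × 0.01 = 1.106; √DE = 1.051; 1.96/1.051 = 1.864; two-sided tail 6.2%; shortfall 1 − 1/1.051 = 4.9%.

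**Step 3: simulation of a centre-only model with no treatment effect.**

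- *21 teams, assumed 7 centres of 3.* Across several simulations, type I error was 4.8–5.0% at ICC 0, 5.8–6.5% at 0.01, 8.1–9.3% at 0.03 and 9.6–11.4% at 0.05. The result at ICC 0 shows that the excess comes from team clustering.
- *18 teams of 12, assumed 9, 6 or 3 centres, centre ICC 0.01, 4,000 runs per setting.* Type I error was 6.5–7.1% at team ICC 0.01, 8.3–10.1% at 0.03 and 11.4–12.5% at 0.05. Monte Carlo standard error near 6.5% is √(0.065 × 0.935/4000) = 0.4 percentage points.

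**Step 4: team level put in.** In the 18-team simulations, a random intercept for team with a t reference on 18 − 2 = 16 degrees of freedom gave 2.8–4.5%, so at or below the nominal level.

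**The case against.** The strongest reply is that no centre-only model is specified. The sentence says what mixed models can do and speaks of levels in the plural. It does not list the random effects, call centre the only level or rule out a team level, and the full list may stand in a statistical analysis plan that is not shown. This stands, and it makes the inflation conditional. A reader might infer that the planned analysis ignores the randomised unit and that its type I error does exceed 5%; the protocol does not support that. What survives is that the protocol names a level, and it is not the randomised one. That differs from leaving a detail open.

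The word for centre may also be loose usage for team. The section on treatment as usual moves from centres to FACT-teams within a few lines, and the sample size shows that the authors knew the clustering unit. A drafting slip is plausible. However, the randomisation section uses the two words for different levels, so the analysis sentence cannot safely be read as meaning teams.

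The excess is modest at the protocol's own ICC. That is true: about one to two percentage points. The larger figures need ICCs that are not in the document.

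Finally, a reader might infer that with about 20 clusters the planned test is too liberal because it relies on a normal reference distribution. The protocol names no reference distribution or degrees of freedom, so this cannot be held against it. The small number of clusters is a reason for advice on the method only.

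**Conclusion.** The concern holds as an inconsistency. The clustering level named in the analysis is the stratification factor, while the randomisation and the sample-size ICC are both at FACT-team level. It should be corrected, because it touches the primary test and carries over to the secondary outcomes.

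The consequence applies only if centre is fitted as the sole cluster level. At the protocol's ICC of 0.01, type I error is then about 6–7% and standard errors are about 4–5% too small (about 6% if all 260 planned patients were analysed in 18 teams). For the 21 teams that joined, it is about 8–9% at an ICC of 0.03 and 10–11% at 0.05; the 18-team scenarios run somewhat higher. The direction follows from the design. The size rests on the true team ICC, on equal team sizes and, for the simulations, on an assumed number of centres. The 0.01 is itself a planning assumption, whereas a model with a team intercept estimates the team variance from the data.

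**What to change.** Replace the clustering sentence in the Statistical analysis section with wording such as: *The linear mixed models include a random intercept for FACT team, the unit of randomisation, with repeated weights nested within patients and centre included as the stratification factor. The same structure applies to the secondary outcomes, with logistic mixed models where needed.*

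Naming the team level resolves the inconsistency. With only 18–21 clusters, it is also advisable to state a small-sample degrees-of-freedom method for the linear models, for example Satterthwaite or Kenward-Roger.

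**Cost.** No new data are needed: the study number already carries a three-digit FACT-team code (Protocol, section 2.1). Intervals become slightly wider. The list of changes at the front of the protocol already speaks of results, so if an analysis was run without the team level, it has to be re-run and not just reworded.

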In the Netherlands patients with SMI can be treated by FACT-teams. FACT opts to provide services to the whole group of people with SMI and provide long-term care for people with SMI who are not in psychiatric hospitals. Care by FACT includes management of illness and symptoms (treatment), guidance and practical assistance with daily living, rehabilitation and also recovery support. FACT teams are multidisciplinary teams which can include psychiatrists, nurses, psychologists, employment specialist, peer support workers and social workers.

THE INTERVENTION

The intervention is primarily modelled after the successful STRIDE intervention [10]. The STRIDE lifestyle intervention, was developed for persons with SMI and was effective in reducing weight and cardiovascular risk factors. The STRIDE intervention was based on prior research (PREMIER clinical trial) [19], behaviour change theories such as the trans theoretical model [20, 21] and motivational theory [22-24]. The basis of the STRIDE intervention will be used in the SMILE study. Additionally, when included patients are current smokers, attention is given to smoking cessation. This was not included in the original stride intervention. Patients who want to quit smoking will be directed to their general practitioner or treating physician. They will be offered standard smoking cessation care that is frequently offered.

The SMILE intervention will be carried out by health care workers the FACT-teams. This could include nurses, health care workers, peer support workers or similar disciplines.

The proposed tailored lifestyle intervention lasts 12 months and consists of (A) the initial intervention (first 6 months), and (B) the maintenance phase (second 6 months).

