293	Additionally, the EQ-5D-5L will be used to compute quality adjusted life years. The EQ-5D-5L rates
294	self-care, mobility, pain, psychic functioning (anxiety/ depression), and usual activities on a 5-point
295	scale. The patients' EQ-5D-5L health states will be converted into utility scores using the Dutch tariff
296	QALYs will subsequently be calculated using linear interpolation between measurement points.
297	Health related self-efficacy
298	The Patient Activation Measure (PAM-13) is a reliable questionnaire which contains 13 items derived
299	from the original PAM-22 [28]. The questionnaire assesses patients' self-reported knowledge, skills
300	and confidence for health related self-efficacy.
301	
302	COSTS
303	Costs questionnaire
304	Cost questionnaires will be completed at baseline, after 6 months and after 12 months. Questions are

305	based on the TiC-P [29] and will include health care utilization, work absenteeism and presenteeism,
306	and sports. Mental health ward admissions and medication use, including medications taken that affect
307	weight, mood stabilizer medication use and anti-depressant medication use will be used as well.
308	Information regarding medication use is used from the pharmacy of the Patient. Of this patients are
309	informed in the patient information letter and will be asked to give their pharmacy information to the
310	assessor.
311	
312	Other study parameters (if applicable)
313	
314	DEMOGRAPHIC DATA
315	Demographic data (ethnicity, age, gender, marital status, employment status, education, diagnosis of
316	SMI, time in care in FACT-team) will be collected directly from the patient records.
317	
318	SMOKING STATUS
319	Patients will be asked if they are current smokers and, if so, how many cigarettes they smoked in the
320	last 7 days. Additionally, at 6 months and 12 months follow-up measurements patients who mentioned
321	to be current smokers will be asked if they participated in a smoking cessation program (such as a
322	smoking cessation intervention) or another kind of help for smoking cessation (such as guidance by a
323	caregiver or physician).
324	
325	LIFESTYLE FACTORS
326	Physical activity and nutrition status will be asked by one question using a VAS-scale concerning the
327	past 4 weeks.
328	
329	COMPLIANCE
330	During the intervention phase intervention appointments not attended (no-shows) will be assessed by
331	the staff of the according FACT-Team.
332	

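### Part of the primary model's covariate set is decided by significance tests of baseline differences, next to an open covariate list, and baseline weight is never named

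*Protocol*

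**What the plan says.** In the Protocol, Statistical Analysis, baseline characteristics are compared "to determine whether randomization was successful; i.e., to assess if balanced groups were obtained after randomization". Under Primary study parameter(s), the hypothesis is that the intervention is superior "in reducing weight loss (primary outcome) over time, linear mixed models will be used".

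Two sentences in that paragraph then govern the covariates:
- "The main analysis will consist of fully corrected models, which will be corrected for significant differences between the two groups at baseline".
- "We will include gender, age, and other variables that are known to affect weight as covariates in all analyses".

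The second sentence applies whatever any test shows, but only age and gender are named. Baseline weight is not named. The text does not say whether it enters as a covariate, as the first repeated measurement or through a change score. Centre is the stratification factor (Randomisation) and appears in the analysis only as a level that mixed models can add for clustering. Secondary outcomes are analysed in the same way as the primary.

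On timing: "Before persons with SMI are recruited, participating FACT-teams will be randomly allocated to serve" as intervention or control teams. Team members, who cannot be blinded, then select and approach patients (Recruitment and consent).

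**The concern.** A covariate earns its place through its relation to the outcome. Whether its difference between arms reaches p < 0.05 says little about that. A rule based on baseline significance has three consequences:

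- A strongly prognostic variable that differs, but not significantly, gets no correction through this rule.
- A variable unrelated to weight can enter because of a chance difference.
- The model behind the primary estimate is known only after the data have been inspected. The open list of weight-related variables adds to this.

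The design sharpens the point. With recruitment after allocation by staff who know the arm, baseline differences need not be chance alone. A test of baseline differences is then neither a check of the randomisation nor a good screen for what to adjust. Because secondary outcomes follow the same method, the rule reaches them as well.

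**Working it through.** **Inputs from the Protocol.** Difference 4 kg, SD 10, alpha 0.05 (taken as two-sided), power 0.80, 100 per group, 20% dropout (Sample size calculation); 224 patients included (changes to the original protocol).

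**The plan's own figure.** n per arm = 2 × (1.960 + 0.842)² × 10² / 4² = 98.1, rounded up to 99, against 100 stated. It reproduces.

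**Chance entry.** For k independent, truly balanced variables tested at 5%, P(at least one enters) = 1 − 0.95^k: 23% for k = 5, 40% for k = 10, 54% for k = 15. A balanced baseline weight would be picked by the test about 5% of the time.

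**Effect on the primary test.** The documents give no SD for baseline weight, so it is assumed, with a range. SD 10 is read as the SD of the weight change. With equal SD s at both times, 10² = 2s²(1 − r), so r = 1 − 50/s². Completers: 224 × 0.8 / 2 = 89.6, about 90 per arm. The residual SD is s for 12-month weight alone, 10 for change, and s√(1 − r²) with baseline weight always in the model (9.1 at s = 12, 9.7 at s = 20).

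Simulated power for 4 kg (20,000 runs per setting, individual level, no clustering, baseline weight as the only covariate, added only if its baseline p < 0.05):

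| Baseline SD (kg) | r | 12-month weight, test-driven | Change, test-driven | Baseline weight always in |
|---|---|---|---|---|
| 12 | 0.653 | 62% | 76% | 83% |
| 15 | 0.778 | 44% | 77% | 80% |
| 20 | 0.875 | 28% | 77% | 79% |
| 25 | 0.920 | 20% | 76% | 77% |

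Type I error under the test-driven rule was 2.2% to 3.9% for 12-month weight and 4.5% to 5.1% for change, against about 5% with baseline weight always included. The rule is conservative or neutral, not anti-conservative.

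**Imbalance left uncorrected under a change score.** With 112 per arm (224 / 2) and s = 20, the largest non-significant difference is 1.96 × 20 × √(2/112) = 5.2 kg. It shifts the change estimate by (1 − 0.875) × 5.2 = 0.65 kg. The same arithmetic gives 1.09 kg at s = 12 and 0.52 kg at s = 25. A one-standard-error imbalance at s = 20 (2.7 kg) shifts it by about 0.33 kg.

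**The case against.** The strongest reply is that the two covariate sentences add up. Age, gender and weight-related variables are in every analysis, and significant differences only supplement them. Baseline weight can fall within the open list, be the first measurement in a model over time, or be absorbed by a change score. This stands. A reader might infer that baseline weight is adjusted for only if it differs significantly, but the protocol does not say so. Its fault is that it does not say how baseline weight enters.

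It can also be said that the large power losses belong to the less well supported reading. The outcome is labelled weight loss, the coefficients are described as a reduction in kilograms, and the sample size concerns weight reduction. This stands too. Change is the better supported outcome, and the 12-month-weight column is a bound on what the wording permits, not a forecast.

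A further tempting inference is that follow-up smoking or medication will be used as covariates and adjust away part of the effect. Both are recorded at 6 and 12 months. The cost questionnaire covers "medication use, including medications taken that affect" weight, and "when included patients are current smokers, attention is given to smoking cessation". But no section says that follow-up values will be covariates. The wording merely fails to exclude them, so this supports one clarifying clause and no claim of bias.

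Finally, an unseen statistical analysis plan may list the covariates. That would answer the open list. It would not answer the significance rule, which the protocol itself fixes for the main analysis.

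**Conclusion.** The point holds in limited form. The protocol makes part of the primary model depend on baseline significance tests, leaves the rest of the covariate list open, and does not fix the role of baseline weight or name centre as a covariate.

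On the better supported reading, in which change is analysed, the harm is modest: 1 to 7 percentage points of power over assumed baseline SDs of 25 down to 12 kg (2 points at 20 kg). The shift at the edge of significance is about 0.5 to 1.1 kg over the same range, against a 4 kg target. If 12-month weight were modelled without guaranteed baseline adjustment, power could fall to 62% to 20%. There is no type I inflation on either reading.

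These figures rest on the assumed baseline SD, equal SDs at both times, independent patients and a single covariate. The case for change does not need the worst figure: a prespecified rule is better on every reading and costs almost nothing.

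**What to change.** Delete the rule based on significant baseline differences and replace both covariate sentences with one statement:

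- The primary model adjusts for baseline weight, centre (the stratification factor), age and gender, plus weight-related variables listed by name, irrespective of any baseline difference.
- All covariate values come from the baseline assessment before the intervention starts. The limit should be worded this way and not as before allocation: teams are allocated before patients are recruited, so a ban on variables measured after allocation would exclude baseline weight itself.
- Each secondary outcome is adjusted for its own baseline value where one is measured.
- The baseline table stays descriptive and does not select covariates.

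Baseline weight, age, gender, smoking and medication are already scheduled at baseline and centre is known, so no new data are needed. The note on changes to the protocol already refers to the trial's results. If the outcome data have been seen, the prespecified-covariate model can no longer replace the primary analysis. Report it as a labelled sensitivity analysis beside the protocol-specified model, and state which covariates the significance rule brought in.
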